7.8.3. Clinical Laboratory

Hematology and biochemistry parameter values will be summarized separately for the single-dose and the multiple-dose phase using descriptive statistics for observed and change from baseline values at the EOT/ET visit.

Additionally, shift tables will be provided. The shift in laboratory results at EOT/ET (i.e., low, normal, high) from baseline classification will be summarized using frequency and percentages. Hematology, biochemistry, and urinalysis parameter values will be listed by subject.

7.8.4. Height, Body Weight and BMI

Baseline height, weight, and BMI will be summarized and listed.

7.8.5. Vital Signs

Vital signs values (i.e., systolic and diastolic blood pressure, pulse, respiratory rate, body temperature and oxygen saturation (%)) will be summarized separately by the single-dose phase and by the multiple-dose phase using descriptive statistics. The observed values and change from baseline at all post-baseline assessment visits and at the EOT/ET visit will be presented. Vital sign values will be listed by subject.

7.8.6. Physical Examination

Physical examination results (by body system) at baseline and EOT/ET visits will be presented separately for the single-dose phase and the multiple-dose phase using frequency and percentages.

A subject listing will be presented for the physical examination results (by body system).

7.8.7. 12-lead ECG

A subject listing of 12-lead ECG results will be provided.

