14.6.6. Physical Examination

For each body system, the number and percentage of subjects with transitions from normal or not done at baseline to abnormal post-baseline will be presented by treatment group. The percentages will be calculated relative to the number of subjects having normal or missing assessments at baseline who also had a post-baseline physical examination. A listing of physical examination data for all subjects will also be provided.

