3.11. Physical Examination

A complete physical examination (by body system) was conducted at Screening or pre-dose evaluation. A brief physical exam excluding height and weight was performed at the EOT assessments. The physical examination evaluation included an examination of abdomen, extremities, general appearance, genitourinary, heart, HEENT, lungs, lymphatic, musculoskeletal, neck, neurological, skin, thorax and other conditions of note. Physical examination findings were recorded as normal, abnormal or not done.

Clinically significant abnormalities (as per Investigator’s or Sponsor’s criteria) in physical examination findings were to be considered as an AE or SAE as appropriate.

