8. CHANGE FROM PROTOCOL

This SAP is based on Amendment 05 to Clinical Study Protocol, 01 April 2019. Since the study was terminated early and the abbreviated CSR will only include the safety analyses. The efficacy and PK analyses described in the protocol will not be conducted.

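### SAP 7.8.6 does not specify the protocol's count of new physical examination abnormalities, and SAP section 8 does not declare the change

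*SAP*

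**What the plan says.** Protocol 14.6.6 defines the physical examination summary system by system and within subject: "the number and percentage of subjects with transitions from normal or not done at baseline to abnormal post-baseline will be presented by treatment group". Its denominator is taken "relative to the number of subjects having normal or missing assessments at baseline", and is limited to those with an examination after baseline. A listing is added.

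SAP 7.8.6 reads: "Physical examination results (by body system) at baseline and EOT/ET visits will be presented separately". The split is by study phase, single-dose and multiple-dose, and the results are given as frequencies and percentages. It keeps a subject listing by body system. It mentions no transition, no shift and no at-risk denominator.

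SAP section 8 names one departure from the protocol's analyses: "The efficacy and PK analyses described in the protocol will not be conducted". It presents the abbreviated report as containing the safety analyses.

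Elsewhere the SAP does specify within-subject comparisons. For laboratory data, section 7.8.3 states: "The shift in laboratory results at EOT/ET (i.e., low, normal, high) from baseline classification will be summarized using frequency and percentages". Vital signs (7.8.5) and the sedation score (7.9.1) are to be reported as change from baseline.

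**The concern.** Safety is the only subject of this SAP, and section 8 gives a reader no reason to think that any protocol safety summary has been altered. For physical examination, the summary as written is a different one. The protocol's table answers how many infants acquired an abnormality in a given system. Frequencies at each visit answer how many were abnormal on each occasion. The two differ whenever some findings resolve while others appear, because the changes offset each other in the visit totals. At stake is a summary table that could show no net change in a body system although individual infants had changed.

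**Working it through.** No planned figure depends on this point, so there is none to reproduce. The check is a comparison of the texts, then a short calculation.

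**Texts side by side**

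| Element | Protocol 14.6.6 | SAP 7.8.6 |
|---|---|---|
| Quantity | Subjects moving from normal or not done to abnormal | Results at baseline and at EOT/ET |
| Denominator | Normal or missing at baseline, with a later examination | None given; SAP 6.1 uses non-missing values at each visit |
| Within-subject link | Yes | Not specified |
| Listing | Yes | Yes |

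SAP section 8 records no change on this row of the safety analyses.

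**What visit totals can and cannot show**

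Let N infants have the system examined at both visits. Let B be the number abnormal at baseline, E the number abnormal at EOT/ET, W the number newly abnormal and R the number resolved. Then

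E = B − R + W.

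The SAP frequencies give N, B and E. With R and W both unknown, one equation does not fix W. Since R lies between 0 and B, and W cannot exceed N − B,

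max(0, E − B) ≤ W ≤ min(E, N − B).

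The documents contain no examination results, so the counts of abnormal infants below are assumed. The values of N are planned sizes: 5 is one single-dose cohort (and the number enrolled in Group B, SAP 3.1), and 15 is the single-dose maximum for an age group (SAP Table 3).

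- N = 5, B = 1, E = 1. The visit table reads 1/5 (20.0%) twice. W runs from max(0, 0) = 0 to min(1, 4) = 1, so the new-abnormality proportion is 0/4 (0%) to 1/4 (25.0%).
- N = 5, B = 2, E = 2. The visit table reads 2/5 (40.0%) twice. W runs from 0 to min(2, 3) = 2, so the proportion is 0/3 (0%) to 2/3 (66.7%).
- N = 15, B = 3, E = 3. The visit table reads 3/15 (20.0%) twice. W runs from 0 to min(3, 12) = 3, so the proportion is 0/12 (0%) to 3/12 (25.0%).

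In these examples every infant is examined at baseline, so the protocol's denominator equals N − B. A shift table gives W directly, and R then follows as B + W − E.

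**The case against.** The strongest reply is that little is lost. It has several parts.

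- **Traceability.** The by-subject listing is retained, and with cohorts of 5 to 10 infants a reader can follow each child. Under SAP 3.11, clinically significant findings become AEs or SAEs, and these are tabulated under 7.8.2. Respiratory rate, oxygen saturation, apnea and sedation have their own summaries. This stands. A reader might infer that new abnormalities would be hidden from the report; the documents do not support that. What is missing is the summary count, which matters mainly for abnormalities not judged clinically significant.
- **The protocol's own inconsistency.** Its synopsis promises only a listing of physical examination findings. This also stands and weakens the charge, although 14.6.6 is the detailed specification and the synopsis does not exclude a table.
- **Unseen layouts.** SAP section 11 places the table shells in Module 2, which is not available here. A cross-tabulation there cannot be ruled out. The supportable statement is that the SAP text does not specify one.
- **The word separately.** It might be read as splitting the two visits. In the full sentence it splits the two study phases, so nothing here rests on it.
- **The brief EOT examination.** SAP 3.11 says: "A brief physical exam excluding height and weight was performed at the EOT assessments". One might infer that fewer systems were examined at EOT, so that the two visits describe different infants. The text excludes only height and weight, and the inference goes beyond it.
- **Attribution.** A transition need not be a drug effect. Protocol 8.1.1 and 8.1.2 allow the baseline examination before, during or after surgery, so for some infants a new finding may reflect the operation. The single-dose phase has no concurrent control. This limits interpretation of the restored table but does not remove the discrepancy.

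**Conclusion.** The point holds in a limited form. SAP 7.8.6 does not specify the protocol 14.6.6 transition count, and SAP section 8 does not declare that change to a safety analysis. Visit frequencies cannot replace the count: in the middle example, identical 40% figures are compatible with anything from none to two-thirds of the infants at risk becoming abnormal. That range shows what the table format leaves open. It is not an estimate for this trial, because the counts are assumed.

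The consequence is modest. No estimate, test or dosing decision depends on the table, and the individual data remain in the listing. A reader might go further and conclude that the protocol's safety result is unrecoverable or that emerging harm would be missed; the retained listing and the adverse event recording rule that out. The conclusion assumes that the unseen shells follow the SAP text. If they already contain a cross-tabulation, only the wording of 7.8.6 needs correcting.

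**What to change.** In SAP 7.8.6 add a baseline-to-EOT/ET shift table by body system. Present it by phase and in the SAP 6.4 groupings: age group and dose group for the single-dose phase, age group and treatment group for the multiple-dose phase. Give n (%) going from normal or not done at baseline to abnormal afterwards, with the protocol 14.6.6 denominator: infants normal or missing at baseline who had a later examination. The change from not done to abnormal may be shown on its own row as extra detail, but those infants should stay in the protocol's numerator and denominator. Keep the listing.

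If the table is not to be produced, SAP section 8 should say so and give the reason.

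The cost is one table and its shell, from data already collected, plus a few lines of SAP text. No protocol change is needed.

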7.9. Other Safety Parameters

7.9.1. Respiratory and Neurological Function

The respiratory and neurological function assessments will be summarized separately for the single-dose phase and the multiple-dose phase.

The following will be summarized using frequency and percentages:

- Were any episodes of apnea observed?
- If apnea observed, was the episode considered to be an adverse event?
- Was sedation noted?
- If sedation noted, was sedation considered as an adverse event?

Modified Ramsay Sedation Scale scores will be summarized using descriptive statistics for observed and change from baseline at all post-baseline assessment visits and at the EOT/ET visit. Additionally, the level of sedation will be summarized using frequency and percentages.

A subject listing of respiratory and neurological functions will be presented. Oxygen saturation and Modified Ramsay Sedation Scale scores along with level of sedation will also be listed.

7.10. Pharmacokinetic Analysis

Only safety analyses are being conducted for this abbreviated CSR, hence no PK analyses will be conducted.

8. CHANGE FROM PROTOCOL

This SAP is based on Amendment 05 to Clinical Study Protocol, 01 April 2019. Since the study was terminated early and the abbreviated CSR will only include the safety analyses. The efficacy and PK analyses described in the protocol will not be conducted.

9. REVISION HISTORY

This is the first version of the SAP. Non-editorial changes made to any of the modules of this SAP will be recorded as necessary as revision history.

11. TABLES, LISTINGS, AND GRAPH SHELLS

The layouts of the summary tables, subject listings, and graphs are presented in SAP Module 2. These layouts incorporate all the appropriate table titles, table numbers, and footnotes.
